6 STUDY SETTING

York and Scarborough Teaching Hospital Foundation Trust NHS Hospital is the primary study site. Although the three workstreams will include participants from across the country, the design of the study does not require the opening of multiple research sites as the majority of data will be collected online and there is no change to patient care. The location of the in-person workshops in WS3 will be selected considering accessibility and suitability for the planned activities. These do not need to necessarily be held within NHS facilities and this has been budgeted accordingly.

Recruitment of participants is described in more detail in section 7 but can be undertaken centrally. Participants will be accessed via an advertising strategy supported by charitable and professional organisations as detailed in section 7.

FUNDED BY

National Institute for
Health and Care Research

York and Scarborough
Teaching Hospitals
NHS Foundation Trust

UNIVERSITY
of York
Est. 1841
YORK
ST JOHN
UNIVERSITY

MenSH-IBD

7 SAMPLE AND RECRUITMENT

7.1 Eligibility Criteria

	Inclusion	Exclusion
Men with IBD	A diagnosis of Crohn's Disease, Ulcerative Colitis or IBD-U. Identify as male	Unable to provide informed consent. Less than 18 years old.
Partners of men with IBD	Currently in (or in the last 5 years) an intimate partnership with a person who identifies as male and has a diagnosis for Crohn's Disease, Ulcerative Colitis or IBD-U.	Does not speak English. Not able to participate in the research activity (interview, focus group or workshop).
IBD service manager	An NHS employee whose current employment involves oversight of the delivery and provision of a secondary care IBD patient service within their employing organisation. This may be a healthcare professional or non-clinical manager.	
IBD nurses	A registered nurse who as part of their role is responsible of the provision of care to patients with IBD.	
IBD health professionals	A health professional registered with the GMC, NMC or HCPC who's professional role is considered part of the IBD multidisciplinary team. Currently or previously employed in a role that directly provides care, support or advice to men with a diagnosis of IBD.	
IBD stakeholders	A representative of a charitable, not-for profit, professional, public or governmental organisation that is engaged with men who suffer from long term conditions or IBD specifically.	

7.2 Sampling

7.2.1 Size of sample

WS1. Cross-Sectional Surveys

(WS1.1) For the survey of NHS IBD services, the **target sample size is 114**. Population estimates have been based on the information provided in the IBD-UK 2019/20 audit report which had a response rate of 72% (IBD-UK, 2021). In a personal communication, IBD-UK confirmed that the response rate for the most recent audit (not yet published) is 66%. Given the current NHS pressures, sample size calculations have been based on a lower response rate of 50% of the 228 services. Given the current NHS staffing challenges, we anticipate the response rate to our survey will be lower and have based our sample size calculations on a response rate of 50% (which we think is a conservative estimate). A response rate of 50% would allow estimation of key binary indicators (assuming a 50% proportion, which is the worst-case scenario) with a margin of error (MoE) of 6.5% for a 95% confidence level (CL).

(WS1.2) For the IBD nurses survey the **target sample size is 90**. The findings from the Caseload Report Standards for IBD Specialist Nurses in the UK (Crohn's & Colitis UK, 2017) and the survey by Leary and colleagues (Leary et al., 2018) estimated that there are 300 IBD nurses in the UK. The estimate was based on national data curated from the IBD audit and the Crohn's and Colitis UK. The response rate for that survey by Leary et al. (2018) was 55% (168 responses received). As the survey was conducted in 2017 and given the impact of the COVID-19 pandemic and ensuing challenges in the IBD workforce as highlighted in the survey by Kennedy et al (2020) of IBD services across the UK, we have assumed that the response rate might be lower and have assumed it to be 30%. A response rate of 30% (n=90) would allow estimation of key binary indicators (assuming a 50% proportion) with a margin of error (MoE) of 8.7% for a 95% confidence interval (CI). If instead the response rate is 20% (n=60) then the MoE increases to 11.3%.

(WS1.3) An estimated total **sample size of 378** adult male respondents is required to provide an estimate for the proportion of IBD patients who have had their sexual health needs assessed or discussed with an IBD clinician, with a margin of error of 5% and 95% CL. The IBD-UK survey (IBD-UK, 2021) was completed by approximately 3236 adult male respondents over the course of seven months; this survey will also run for seven months. It is anticipated that the number of respondents will be lower than that of IBD-UK survey for adult male respondents. At 4 months a review of recruitment numbers will occur. If the number of respondents is less than 50% of the target, then the recruitment strategy will

FUNDED BY

National Institute for
Health and Care Research

York and Scarborough
Teaching Hospitals
NHS Foundation Trust

Est.
1841
YORK
ST JOHN
UNIVERSITY

MenSH-IBD

be amplified. Any responses received beyond 378 would enable us to estimate this proportion with further accuracy and potentially enable us to provide reliable estimates stratified by various characteristics such as age group, sexuality and ethnicity.

WS2. Qualitative study

(WS2.1) An estimated sample size of 15-20 participants, determined by data saturation (Hennink et al., 2017). This number will enable a heterogenous sample sufficient to address our research question, taking into consideration variation in disease presentation and possible variation in participant demographics including age, race, sexual orientation, and relationship status.

(WS2.2) 6-8 participants per focus group, with a total of three independent groups. This group number will allow diversity in the professional groups and stakeholders participating while safeguarding effective running, facilitation, and output of the workshop.

WS3 Co-production workshops

The estimated sample size is 8-12 participants who will participate in three sequential workshops. This allows for variation in public, stakeholder and professional representation while ensure facilitation of the workshop if effective leading to tangible outputs.

7.2.2 Sampling technique

WS1. Cross-Sectional Surveys

(WS1.1) Census approach of all IBD services as identified by the 2019 IBD-UK audit.

(WS1.2) Census approach of all IBD specialist nurses.

(WS1.3) Targeted convenience sampling of men with IBD via established networks.

WS2 and WS3 Qualitative study and co-production workshops

Purposive sampling will be adopted in workstreams 2 and 3. For the interviews a heterogenous sample who indicate a willingness to be interviewed in the patient survey in WS1 will be purposively recruited based on a range of characteristics including age, ethnicity, marital/partner status, sexuality, and IBD type (UC or Crohn's). Participants with partners will be asked to invite them to participate should they wish. For the focus groups a multidisciplinary sample of participants (e.g., nurses, doctors, allied health professionals, psychologists) involved in the provision of IBD care in the NHS setting will be purposively recruited.

7.3 Recruitment

WS1. Cross-Sectional Surveys

To identify and sample respondents we will use social media. For surveys WS1.1 and WS1.2, we will also replicate the approach taken by the national IBD-UK audit, last completed between July 2019-January 2020 (IBD-UK, 2021). IBD-UK have identified all 228 secondary care IBD services in the UK and have provided us with this list so that we are able to contact services directly via email. For survey WS1.3, we will also identify and sample respondents through the membership of Crohn's and Colitis UK's (CCUK) (n~50,000), advertising the survey via their website, e-newsletters, and distributing it via wider networks and partners, e.g. promoting the survey in geographic regions with a high density of under-represented groups or those less likely to be exposed to traditional and online focused methods of study advertising. CCUK have established procedures for advertising research to their membership group and have already agreed to distribute the survey when ethical approval is received. This approach has been previously successful in several IBD-UK surveys of patient experience, yielding >10,000 patient responses. We will also ask all the IBD services contacted in the first two surveys to advertise the study using posters, leaflets, social media and other methods. Patients scheduled for appointments who meet the inclusion criteria may receive the study poster with their appointment information, or the poster may be given out at appointments by IBD nurses. During normal working hours, a member of the research team will be available to answer any questions. If the number of respondents is less than 50% of our target, then we would amplify our recruitment drives to target populations that are under-represented and achieve the required sample size. This could include promoting the study in particular geographical regions or through specialist community groups, or using channels and connections made by CCUK in their attempts to tackle under-representation in their membership group and research, where feasible.

WS2 and WS3 Qualitative study and co-production workshops

During the WS1 surveys there will be the opportunity for respondents to express an interest in participating in WS2 and WS3. From those who express an interest a heterogenous sample of approximately 15-20 men (based on a range of characteristics including age, ethnicity, marital/partner status, sexuality, IBD type) will be invited to participate. We will also recruit participants by advertising the study using posters, leaflets, social media and online methods. A similar approach will be utilised with the focus groups and will also include an element of snowball sampling of professional colleagues. To ensure the focus groups and workshops are attended by a range of stakeholders and professionals we will advertise the study through professional networks. This approach will enable us to access a

FUNDED BY

National Institute for
Health and Care Research

York and Scarborough
Teaching Hospitals
NHS Foundation Trust

Est.
1841
YORK
ST JOHN
UNIVERSITY

MenSH-IBD

larger, more diverse sample, whilst also mitigating time and cost constraints associated with setting up multiple NHS study sites within the region, and removing the effect of variations in how different NHS Trusts manage their IBD caseload.

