4.1 Objectives

- Identify how the sexual health of men with IBD is currently assessed and cared for by specialist nurses in the NHS.
- Gather ideas on appropriate and acceptable ways in which men's sexual health care in IBD could be improved.
- Co-produce a prototype intervention to improve the assessment and care of the sexual health needs of men with IBD.

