A national cross-sectional survey of IBD nurses working in the 228 known adult services in the UK. The survey will be distributed to IBD nurses working in each service via the clinical lead/service managers contacted in 1.1 and via the Royal College of Nurses IBD network, CCUK and IBD Specialist Nurse regional meetings and conferences. Advertising the survey will be repeated at different intervals within a 6-month period to improve visibility. There will be a direct follow up with clinical leads when there has been no nurse response. The survey will cover several domains, including the current practice, assessment tools, facilitators, barriers, and confidence in delivering sexual health assessment, care, and advice to male patients with IBD.

(WS1.3) Survey of male IBD patients

A cross-sectional national survey of men with IBD across the UK. The survey will be mainly distributed with the support of CCUK and social media networks. The NHS sites identified in survey 1.1 will be asked to display adverts for the survey but will not act as participant identification sites. The survey will

FUNDED BY

National Institute for
Health and Care Research

York and Scarborough
Teaching Hospitals
NHS Foundation Trust

Est.
1841
YORK
ST JOHN
UNIVERSITY

MenSH-IBD

cover several domains, including the experience of sexual health care assessment and intervention, and perceived needs, preferences, and barriers.

Analysis of quantitative data

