Data will be analysed descriptively using appropriate summary statistics (frequencies/percentages for categorical variables; means/standard deviations or medians/quartile ranges for continuous variables, depending on their distribution). For key variables and scores, 95% confidence intervals will be presented and differences between geographical regions evaluated. Differences between centres that responded and those that did not will be tested using available information. Several associations including barriers and facilitators with the offer of a sexual health assessment for men will be tested using logistic regression. A similar approach will be applied to other key variables and scores as identified by the advisory group and across the three surveys. In each case, estimates of the magnitude of association, for example odds ratio, and corresponding 95% confidence intervals will be presented. Where it is feasible to do so differences between geographical regions and demographic characteristics, such as ethnicity and under-researched populations will be presented. We will assess the mechanism of missing values: if there is a need to impute missing values we will use multiple imputations as a sensitivity analysis.

WS2. Qualitative study

Concurrent with WS1 a qualitative study will be carried out. This will involve: (i) in-depth individual semi-structured interviews with men with IBD and their partners; and (ii) focus groups with nurses and other clinicians involved in the provision of care to men with IBD. The aim of this stream is to explore factors identified in our preliminary PPI work that influence the sexual health assessment and care of men with IBD, and generate ideas on appropriate and acceptable ways in which this could be improved as a basis for the design of the intervention in WS3.

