7.3.2 Consent

WS1: Surveys

FUNDED BY

National Institute for
Health and Care Research

York and Scarborough
Teaching Hospitals
NHS Foundation Trust

Est. 1841 YORK ST JOHN UNIVERSITY

MenSH-IBD

The online survey data is anonymous at point of entry and therefore written informed consent will not be taken. However, the survey will have an opening information page explaining the study and how the data will be used. Participants will be asked to select a box to confirm they have read and understand this information. At the end of the survey there will be two further optional additions (1) to enter a prize draw: participants will be asked to select a box to consent to their contact details to be held separately from the survey responses, only for the purpose of awarding the prize and until completion of the survey, after which all data will be deleted, (2) to express an interest in participating in an interview: participants will be asked to select a box to consent for their contact details alongside the demographic details page to be sent to the study team and stored until the end of the study for the purpose of contact the participant about this study only.

WS2 and WS3: Interviews, focus groups and co-production workshops

Written informed consent will be obtained prior to participation in interviews, focus groups or co-production workshops. The process of obtaining informed consent will be in accordance with Good Clinical Practice (GCP). Participants will be provided with a participant information sheet and given time to consider the information and the opportunity to ask the study team questions. As most of this work will be conducted remotely, on-line consent will be available in this study.

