11 APPENDICES

11.1 Appendix 1- Required documentation

- 11.1.1 Participant Information Sheet
- 11.1.2 Consent form
- 11.1.3 Survey of IBD Services
- 11.1.4 Survey of IBD Nurses
- 11.1.5 Survey of men with IBD
- 11.1.6 Interview guide
- 11.1.7 Focus group guide
- 11.1.8 [name] (CV)
- 11.1.9 [name] (CV)
- 11.1.10 [name] (CV)
- 11.1.11 [name] (CV)

FUNDED BY

National Institute for
Health and Care Research

York and Scarborough
Teaching Hospitals
NHS Foundation Trust

[figure not shown]
UNIVERSITY
of York

EST.
1841
YORK
ST JOHN
UNIVERSITY

MenSH-IBD

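### Does letting IBD nurses hand out the survey poster inflate the WS1.3 estimate of how many men have had their sexual health discussed?

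*Protocol*

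**What the plan says.** The first objective (section 4.1) is to find out how men's sexual health is "currently assessed and cared for by specialist nurses in the NHS". Section 7.2.1 sizes WS1.3 at 378 men to estimate "the proportion of IBD patients who have had their sexual health needs assessed or discussed with an IBD clinician", with a 5-point margin at 95% confidence. It states no look-back period.

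Section 7.3 asks IBD services to advertise the survey. Among the permitted means is that "the poster may be given out at appointments by IBD nurses". Section 5 (WS1.3) sets the balance of routes: the survey is "mainly distributed with the support of CCUK and social media networks". Section 7.2.2 describes the sampling as "Targeted convenience sampling of men with IBD via established networks".

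Section 7.3.2 states that "The online survey data is anonymous at point of entry". On analysis, section 5 says "Data will be analysed descriptively using appropriate summary statistics", adding confidence intervals and logistic regression for associations. The instrument itself is item 11.1.5 of Appendix 1, "Survey of men with IBD". It is named there, but its questions are not in the text at hand.

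**The concern.** The nurses whose care is being measured may also recruit for the measurement, during a consultation, with a poster about sexual health. Receiving a poster is not an assessment, but it can open a conversation. As section 7.2.1 words the proportion, that conversation would count, because nothing there limits it to the time before the man heard of the study.

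Prompting of this kind can only push the proportion up, and a larger sample would not dilute it. Because responses are anonymous, the route by which a man was reached cannot be recovered afterwards unless the survey asks. If the effect were large, the study would overstate current provision, which is what objective 1 sets out to describe, and so understate the unmet need that the intervention in WS3 is meant to address.

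**Working it through.** **The plan's own figure.** With p = 0.5 and d = 0.05, n = 1.96² × 0.25 / 0.05² = 384.1. Section 7.2.1 does not say how 378 was reached. A finite-population correction, n/(1 + (n − 1)/N), gives 378.3 for N = 25,000, which is half of the roughly 50,000 charity members in section 7.3 (taking half as male is an assumption). With N = 50,000 it gives 381.2. The stated 378 is therefore reproduced closely. Without correction, the margin at 378 is 1.96 × √(0.25/378) = 5.04 points.

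**The possible shift.** Let f be the share of respondents reached by nurse handover, c the share of those without an earlier discussion in whom the handover starts one that they then report, and p the true proportion. The upward shift is f × c × (1 − p). The protocol gives none of the three, so the values below are assumptions. Shifts are in percentage points.

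| f | c | p = 10% | p = 20% | p = 50% |
|---|---|---|---|---|
| 2% | 10% | 0.18 | 0.16 | 0.10 |
| 5% | 20% | 0.90 | 0.80 | 0.50 |
| 10% | 30% | 2.70 | 2.40 | 1.50 |
| 20% | 25% | 4.50 | 4.00 | 2.50 |
| 30% | 50% | 13.50 | 12.00 | 7.50 |
| Sampling margin, n = 378 | | 3.02 | 4.03 | 5.04 |

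The first three rows run from 0.1 to 2.7 points, or 0.4 to 10.2 of 378 men, and each entry lies below the margin in its column. The last two rows show what a serious effect needs. To reach 5 points at p = 20% and c = 30%, f = 0.05 / (0.3 × 0.8) = 20.8%, or 79 of 378 men. A fifth to a third of respondents coming from nurses' hands sits poorly with distribution mainly through the charity and social media.

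**The steps needed for any shift.** A nurse chooses to hand over the poster. The exchange goes beyond an invitation and covers that man's own needs. He had no earlier discussion. He completes the survey. He counts that exchange when answering. Only the first step is in the protocol. Section 2 points the other way on the second: it reports, for long-term conditions generally, that nurses lack the time, knowledge and confidence to raise sexual matters, and that men's concerns are rarely considered in IBD nursing care.

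**What a remedy would buy.** A question asking how the man heard of the survey would measure the effect without preventing it. At f = 2%, 5% and 10% there would be about 8, 19 and 38 nurse-handed men. The 95% half-widths at p = 0.5, 1.96 × √(0.25/n), are about 35, 22 and 16 points. Dropping 10% of respondents leaves 340 men and a margin of 5.31 points. It would also drop men with genuine earlier assessments, so it would change the sample without isolating prompting.

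**The case for a change.** The strongest case for acting has three parts.

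1. **The definition is open and a fix is cheap.** Limiting the key item to the time before the man heard of the survey would largely remove the problem, and the source of recruitment cannot be added to anonymous responses later. This is true as far as it goes. However, a recall period belongs in the questionnaire, and section 8.4 has the stakeholder group advise on developing and piloting the WS1 instruments. The protocol does not show that the item lacks such a limit. If the survey is already open, rewording would split the key item into two versions.

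2. **A shift smaller than the margin is not harmless.** A 2-point shift at p = 20% would lower the coverage of a nominal 95% interval to about 85%. The arithmetic is correct, but it supposes a random sample. For volunteers from a charity's membership and social media, selection is already outside what the interval covers, and the net direction of bias is unknown.

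3. **The recruitment text is inconsistent.** Section 7.3 allows scheduled patients who satisfy the eligibility criteria to get the poster with their appointment details. That most naturally means local selection from appointment data. Section 5 says sites are not identification sites, and section 7.3.1 says no NHS patient data are used to identify participants. This tension is real and the passages need reconciling as an editorial matter. It does not contradict the statement that no patient details reach the study team, and it alters no estimate.

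**Conclusion.** The concern does not hold as a fault in the plan. The handover route is real and the sample-size paragraph has no time limit, but the step from there to a biased estimate rests on a questionnaire that cannot be seen and on a chain of events that the protocol does not support. With nurse handover as a minor route (f up to 10%, c up to 30%, p from 10% to 50%, all assumed), the shift is 0.1 to 2.7 points, below the sampling margin in every case. It would become material only if about a fifth or more of respondents came through nurses and handover often led to a first discussion.

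The consequence is limited further because the survey is descriptive and no threshold depends on the proportion. Objective 1 also draws on the service and nurse surveys (WS1.1 and WS1.2), and all findings are triangulated in WS3.1. Handing out posters is a fair trade: it reaches men outside the charity's membership at the price of a small, conjectural distortion. The unstated recall period is ordinary detail for the survey instrument. The inconsistency over local selection is a clerical matter of wording.
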